### 7.1.2 Exclusion Criteria

1. For all groups, participants are ineligible if they meet any of the following exclusion criteria:
  - a. Use of investigational drugs or participation in a clinical drug trial within 30 days prior to any Sampling Visit; or
  - b. Current intoxication, drug or alcohol abuse or dependence; or
  - c. If using any medications or nutraceuticals, the use of inappropriate (e.g., non-prescribed) or unstable dose within 30 days prior to any Sampling Visit; or
  - d. Significant medical, neurological or psychiatric co-morbidity likely, in the judgment of the Site Principal Investigator, to impair participant's ability to complete study procedures, or likely to reduce the utility of the samples and data for the study of HD; or

- e. Needle phobia, frequent headache, significant lower spinal deformity or major surgery; or
- f. Antiplatelet or anticoagulant therapy within 14 days prior to any Sampling Visit, including but not limited to: aspirin (>81mg), clopidogrel, dipyridamole, warfarin, dabigatran, rivaroxaban and apixaban; or
- g. Clotting or bruising disorder; or
- h. Screening blood test results more than 10% outside the lab's normal range for the following: white cell count, neutrophil count, lymphocyte count, hemoglobin (Hb), platelets, Prothrombin time (PT) and activated partial thromboplastin time (APTT), or any combination of blood test results that the Site Principal Investigator deems to be of clinical significance; or
- i. Screening blood test results for C-reactive protein (CRP) >2× upper limit of normal; or
- j. Predictable non-compliance as assessed by the Site Principal Investigator; or
- k. Inability or unwillingness to undertake any of the study procedures; or
- l. Exclusion during history or physical examination, final decision to be made by the Site Principal Investigator; including but not limited to:
  - i any reason to suspect abnormal bleeding tendency, e.g. easy bruising, petechial rash; or
  - ii any reason to suspect new focal neurological lesion, e.g. new headache, optic disc swelling, asymmetric focal long tract signs; or
  - iii any other reason that, in the clinical judgment of the Site Principal Investigator, it is felt that lumbar puncture performed per this protocol and associated manuals is unsafe without brain imaging; or
  - iv positive urine pregnancy test at any screening or sampling visit for females of child bearing potential; or
- m. Lumbar puncture procedure performed for any reason in the previous 30 days; or
- n. Any SAE deemed related to the LP procedure or blood patch necessitated after LP; or
- o. Any other complication or experience during or after any previous lumbar puncture that, in the clinical judgement of the Site Principal Investigator, is likely to pose an unacceptable risk for future lumbar puncture.

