that visit, biosamples will be collected following a fast of at least 6 hours, or overnight: blood will be obtained via venipuncture and CSF will be obtained via lumbar puncture. Some participants may be invited to return for an Optional Repeat Sampling Visit approximately 4-8 weeks after the Annual Sampling Visit during their first year of enrollment.

The annual visits are at regular intervals after the first Annual Screening Visit (i.e. at 1, 2, 3 years and so on)  $\pm$  2 months. Participants will be encouraged to complete all annual visits; however, they are under no obligation to take part and will be able to skip annual visit without being discontinued from the study. Participants who do not come for an Annual Sampling Visit for three consecutive years will be discontinued from the study, but they may enroll again at a later date, if they so consent. Participants who have already completed HDClarity Sampling Visits under earlier versions of this protocol may also participate in the longitudinal study if they meet the eligibility criteria.

Participant cohorts are as follows and recruitment will be balanced across cohorts as far as possible. However, recruitment to the moderate and advanced manifest HD cohorts is expected to be approximately 50% of recruitment to other cohorts and recruitment to the juvenile manifest and incomplete penetrance HD cohorts will be independent of recruitment to other cohorts:

1. Healthy controls
2. Early Pre-manifest HD
3. Late Pre-manifest HD
4. Early Manifest HD
5. Moderate Manifest HD
6. Advanced Manifest HD
7. Juvenile Manifest HD
8. Incomplete Penetrance HD

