### **8.1 Description of Study Assessments**

The Annual Screening and Annual Sampling Visits should be no more than 30 days apart. The Annual Screening Visit may occur on the same day as an Enroll-HD visit. The Optional Repeat Sampling Visit will occur within 4-8 weeks of the Annual Sampling Visit during the first year of enrollment. Participants will be encouraged to complete all annual visits; however, they are under no obligation to take part and will be able to skip annual visits without being discontinued from the study for up to three years.

Information regarding occurrence of adverse events (AEs) and Serious Adverse Events (SAEs) will be captured each year in the period from the Annual Screening Visit until the follow-up phone call after the associated Annual Sampling Visit (or Optional Repeat Sampling visit, if applicable). Duration (start and stop dates and times), severity/grade, outcome, treatment and relation to study procedures will be recorded on the electronic case report form (eCRF).

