**HDCLARITY SCHEDULE OF EVENTS**

Visit Type	Year 0 			Years 1, 2, 3 	
	Annual Screening	Annual Sampling	Optional Repeat Sampling	Annual Screening	Annual Sampling
Visit Window	-30 to -1 days	Day 0	Day 28 - 56	Annually $\pm$ 2 months	Within 30 days of Annual Screening Visit
Study Procedure					
Informed Consent / Assent	X				
Confirm Continued Consent / Assent		X	X	X	X
Inclusion/Exclusion Criteria review	X	X	X	X	X
Demographics update	X			X	
Confirm Enroll-HD core assessments completed within last three months	X			X	
Brief Physical Exam	X	X	X	X	X
Medical History update	X	X	X	X	X
Prior/Concomitant Medication update	X	X	X	X	X
Full Neurological Examination	X			X	
Focused Neurological Examination		X	X		X
Total Motor Score (TMS)		X	X		X
Vital Signs (BP, pulse, body temp)		X	X		X
Safety Laboratory Assessments	X			X	
Urine Pregnancy Test 	X	X	X	X	X
Adverse Events (AE)		X	X		X
Final Eligibility Check		X	X		X
Lumbar CSF Collection		X	X		X
Venous Blood Draw 		X	X		X
CSF and Blood Sample Processing		X	X		X
CSF QC Processing		X	X		X
Telephone Follow-Up within 1-3 days (concomitant medication and AEs)		X	X		X

 This sequence of visits will continue such that Informed Consent/Assent will be sought again every fourth year

 Urine pregnancy test to be performed for females of child bearing potential unless the participant is post-menopausal or not sexually active

 Obtain venous blood sample immediately after CSF collection is complete

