#### **8.1.4 Optional Repeat Sampling Visit**

- This visit is optional. Participant continued consent or assent to participate and eligibility are confirmed and recorded.
- This visit should be scheduled 4 - 8 weeks following the Annual Sampling Visit during the first year of enrollment.
- Participants will be required to fast and drink only water, for at least six hours, or overnight, before the scheduled time of the Optional Repeat Sampling Visit. Compliance with instructions to fast is recorded. If the participant did not fast, they will be sent home, and the procedure rescheduled.

- The results of the routine laboratory examination are reviewed and recorded.
- Urine pregnancy test for females of child bearing potential (excludes females who are post-menopausal or not sexually active).
- Measurement of vital signs.
- Weight measurement (only if weight appears to vary significantly (>3kg/6.5lb) since last Enroll-HD visit).
- Any changes to medical history and medication are noted.
- A focused neurological examination is performed as described in the HDClarity Lab Manual and the brief physical exam is repeated for safety.
- The TMS of the UHDRS is repeated.
- Lumbar CSF Collection is performed. (See Section 9.1 for instructions)
- Venous blood sampling is performed immediately after CSF collection is complete. (See Section 9.2 for instructions)
- AE recording.
- Process CSF, Serum and Plasma samples per Sections 10.1, 10.2 and 10.3, respectively.
- Perform sample QC per Section 12.
- Store samples per Section 11.

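### The 30-day lumbar-puncture exclusion (m), read literally, bars the first two or three days of the Optional Repeat Sampling window, which opens on Day 28

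*Protocol*

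**What the plan says.** Protocol 7.1.2 lists exclusions that apply to all groups, any one of which makes a participant ineligible. Item (m), which also appears in the Synopsis, is a "Lumbar puncture procedure performed for any reason in the previous 30 days". It names no reference visit and makes no exception for punctures done in the study.

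The Annual Sampling Visit is Day 0 and includes a lumbar puncture. The Optional Repeat Sampling Visit includes another. On its timing, 8.1.4 states: "This visit should be scheduled 4 - 8 weeks following the Annual Sampling Visit during the first year of enrollment". Section 8.1 states: "The Optional Repeat Sampling Visit will occur within 4-8 weeks of the Annual Sampling Visit during the first year of enrollment". The Schedule of Events gives the same window as Day 28 to Day 56. The 4-to-8-week interval also appears twice in the Synopsis (Study Design and Sample Size), in 6.1 and in 15.1, so the window is stated in seven places.

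Eligibility is checked again at the repeat visit. The Schedule of Events marks both "Inclusion/Exclusion Criteria review" and "Final Eligibility Check" in that column, and 8.1.4 says: "Participant continued consent or assent to participate and eligibility are confirmed and recorded".

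**The concern.** The two rules give different answers for the same day. A site that books at exactly four weeks follows the visit window, but the exclusion then disqualifies the participant because of the study's own Day 0 puncture.

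A site that applies the eligibility check has to send a fasted participant home and rebook. A site that follows only the window performs an invasive procedure against an exclusion criterion, although for this to happen the eligibility check must also fail. Four weeks is the stated lower bound, so a booking there is foreseeable, and sites in different countries may resolve the ambiguity differently.

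**Working it through.** **Inputs**
- Look-back in (m): 30 days (7.1.2 and Synopsis).
- First puncture: Day 0, the Annual Sampling Visit (Schedule of Events; 8.1.2).
- Repeat window: 4 to 8 weeks in the text, Day 28 to 56 in the Schedule of Events.
- Eligibility review at the repeat visit: yes (Schedule of Events; 8.1.4).

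**The plan's own window.** 4 × 7 = 28 and 8 × 7 = 56, so text and schedule agree. The window holds 56 − 28 + 1 = 29 calendar days.

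**Overlap with the look-back.** On Day d the Day 0 puncture is d days old.

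| Reading of the 30-day limit | Barred days | Share of window | Usable days |
|---|---|---|---|
| Day 30 outside (d < 30) | 28, 29 | 2/29 = 6.9% | 30–56 (27 days) |
| Day 30 inside (d ≤ 30) | 28, 29, 30 | 3/29 = 10.3% | 31–56 (26 days) |

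**Delay to the first eligible day.** With Day 30 inside: 31 − 28 = 3, 31 − 29 = 2 and 31 − 30 = 1 days. With Day 30 outside: 30 − 28 = 2 and 30 − 29 = 1 days.

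**Is any other scheduled pair of punctures affected?** The following are minimum gaps within one continuous enrollment, taken over all calendar start dates.
- *Day 0 to Year 1.* The first Screening is at earliest on Day −30. Year 1 Screening is at earliest 10 months after it (12 months less the 2-month tolerance), which is at least 365 − 62 = 303 days. That is Day 303 − 30 = 273, and Sampling cannot come before Screening. The gap is at least 273 days.
- *Optional Repeat on Day 56 to Year 1.* 273 − 56 = 217 days.
- *Between later annual visits.* Sampling is "Within 30 days of Annual Screening Visit", so Year 1 Sampling is at latest 14 months plus 30 days after the reference Screening. Year 2 Screening is at earliest at 22 months. The 8 months between are at least 365 − 123 = 242 days, so the gap is at least 242 − 30 = 212 days.

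All three are far above 30 days, so the conflict is confined to the Optional Repeat visit.

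**Number of visits affected.** This cannot be derived. The protocol gives a ceiling on invitations (up to about 20% of participants) but no attendance rate and no booking pattern.

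**The case against.** The best defence is that (m) was meant to apply only at entry. Items (a), (c) and (f) tie their look-backs to every sampling visit, and the pregnancy item under (l) names both screening and sampling visits. The drafters named repeat visits when they wanted to, and (m) names none. This reading is possible and would remove the overlap. It does not fit the criteria review and final eligibility check required at the repeat visit. It would also weaken the exclusion, because an outside puncture in the up to 30 days between Screening and Sampling would go uncaught.

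A second defence is that the rules are cumulative. A window sets outer limits, eligibility is a separate condition on each day inside it, and a site can satisfy both on Days 31 to 56. That is true, and it is why the consequence is small. It does not explain why the schedule offers days on which the participant is ineligible.

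Third, the Synopsis softens the lower bound by placing the visit "Optional Repeat Sampling Visit approximately 4-8 weeks after the Annual Sampling Visit during their first year of enrollment". Only that statement is qualified in this way. The Schedule of Events gives Day 28 outright.

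One limit on the check does stand. The 212-, 217- and 273-day gaps hold within one continuous enrollment. Participants who come from earlier protocol versions have no stated minimum interval since their last puncture. Their entry date is flexible, so this creates no second window conflict.

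**Conclusion.** The conflict is real on the literal text, and nothing in the protocol reconciles the two rules. It affects 2 or 3 of 29 window days at one optional visit, depending only on whether Day 30 counts as inside the look-back. The conclusion assumes that (m) is applied again at the repeat visit, which the eligibility re-check supports.

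The severity is low. The re-check should catch most early bookings, no sample pair need be lost, and no safety harm has been shown. This is a drafting inconsistency worth correcting, not a threat to the study.

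**What to change.** At the next routine amendment, make both of these changes together:

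1. Open the Optional Repeat window at Day 31 (Day 31 to 56) in all seven places: Synopsis (Study Design and Sample Size), 6.1, 8.1, the Schedule of Events, 8.1.4 and 15.1.
2. Anchor (m) to the 30 days before any Sampling Visit, in 7.1.2 and in the Synopsis, to match (a), (c) and (f).

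Anchoring (m) without moving the window would only make the overlap explicit. Opening at Day 31 settles the matter whether or not Day 30 counts.

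The cost is 7 + 2 = 9 short edits and at most 3 of 29 window days. A lighter option is a single footnote to the Schedule of Events requiring more than 30 days since the previous puncture. Exempting the study's own puncture, or shortening (m) to 27 days, would keep all 29 days, but only if the sponsor judges that clinically acceptable.

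Section 16.7 requires Sponsor and IRB/ERB approval before any amendment takes effect, so this does not justify an amendment of its own.

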## 7.2 Criteria for Termination of the Study

The Chief Investigator may terminate this study prematurely as follows: (a) on an immediate basis for any reason reasonably related to the health or safety of the participants and (b) upon 90 days written notice to CHDI for any other reason. CHDI may terminate this study prematurely for any reason. The Sponsor and Institutional Review Board(s) (IRBs)/Ethics Review Board(s) (ERBs) must be informed promptly.

If the study is prematurely terminated or suspended for any reason, the Site Principal Investigator/institution should promptly inform the study participants and should assure appropriate follow-up for them.

## **8. Study Procedures**

Participants will attend two annual study visits, an Annual Screening Visit followed by an Annual Sampling Visit. They may also attend an optional visit during their first year of enrollment, an Optional Repeat Sampling Visit. Participants will attend annual visits at regular intervals after the first Annual Screening Visit (i.e. at 1, 2, 3 years and so on)  $\pm$  2 months. The study procedures for each visit type are described in the Schedule of Events table below.

### **8.1 Description of Study Assessments**

The Annual Screening and Annual Sampling Visits should be no more than 30 days apart. The Annual Screening Visit may occur on the same day as an Enroll-HD visit. The Optional Repeat Sampling Visit will occur within 4-8 weeks of the Annual Sampling Visit during the first year of enrollment. Participants will be encouraged to complete all annual visits; however, they are under no obligation to take part and will be able to skip annual visits without being discontinued from the study for up to three years.

Information regarding occurrence of adverse events (AEs) and Serious Adverse Events (SAEs) will be captured each year in the period from the Annual Screening Visit until the follow-up phone call after the associated Annual Sampling Visit (or Optional Repeat Sampling visit, if applicable). Duration (start and stop dates and times), severity/grade, outcome, treatment and relation to study procedures will be recorded on the electronic case report form (eCRF).

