### **Participant risk**

Study-related risks are explained in the informed consent document, including the parental consent for underage participants. In particular, the following risks may be associated with lumbar puncture: pain; headache, infection, bleeding and nerve root damage. Safety data collected in the first two years of HDClarity shows that the overall risk of moderate headache after a lumbar puncture was about 6% and approximately 9% of procedures resulted in mild headaches. The risk of a severe headache was less than 0.2%. Most headaches resolve spontaneously but occasionally a headache may be persistent; in rare cases this may necessitate treatment, which may include a second procedure (a blood patch), carried out in a clinical setting.

See Appendix A – Site Principal Investigator Obligations for additional information.

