#### **8.1.3 Follow-up Telephone Call**

Participants are contacted within 24 to 72 hours following an Annual Sampling Visit to collect any AE and/or concomitant medication data. If an AE is reported and is possibly or probably related to study procedures it must be followed until the event resolves, the condition stabilizes, the event is otherwise explained, or the participant is lost to follow up.

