#### **8.1.5 Follow-up Telephone Call 2**

Contact participant 24 to 72 hours following Optional Repeat Sampling Visit to collect any AE and/or concomitant medication data. If an AE is reported and is possibly or probably related to study procedures it must be followed until the event resolves, the condition stabilizes, the event is otherwise explained, or the participant is lost to follow up.

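### For most lumbar punctures, a non-serious adverse event that starts after the 24-72 hour call has no planned route into the AE data

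*Protocol*

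**What the plan says.** All references are to the protocol.

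- **Window.** Section 8.1 has AEs and SAEs "captured each year in the period from the Annual Screening Visit until the follow-up phone call after the associated Annual Sampling Visit". A parenthesis then moves the end point to the call after the second sampling for those who have one: "or Optional Repeat Sampling visit, if applicable".
- **Call.** Section 8.1.3: "Participants are contacted within 24 to 72 hours following an Annual Sampling Visit to collect any AE and/or concomitant medication data". Section 8.1.5, after a repeat sampling: "Contact participant 24 to 72 hours following Optional Repeat Sampling Visit to collect any AE and/or concomitant medication data". The Schedule of Events agrees: "Telephone Follow-Up within 1-3 days (concomitant medication and AEs".
- **Visits that record AEs.** The AE row of the Schedule is marked at Annual Sampling (Year 0 and Years 1-3) and at Optional Repeat Sampling. It is not marked at any Annual Screening Visit.
- **Eligibility.** Criteria n and o in section 7.1.2 are reviewed at every visit. They cover procedure-related SAEs, blood patches and, in o, "Any other complication or experience during or after any previous lumbar puncture" that the investigator judges to make a further puncture too risky.
- **Known risk.** Under Participant risk, section 4.2.1 gives headache rates from the first two years (moderate about 6%, mild about 9%, severe below 0.2%) and adds that "occasionally a headache may be persistent; in rare cases this may necessitate treatment, which may include a second procedure (a blood patch").

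**The concern.** Lumbar puncture is the study's principal invasive procedure, and headache is the only complication for which the protocol gives a rate. Discharge instructions in 8.1.2.1 foresee headache after the participant has left. Yet under 8.1 the record of non-serious events can close 24 hours after the needle, and the next window looks forward from the following screening visit rather than back to the last puncture.

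Two things are at stake. First, any procedure-related rate drawn from these data counts only events that began before the call, and the length of that observation depends on when the site telephones. Second, a late, non-serious complication can be disclosed at the next eligibility review, and can even exclude the participant, while remaining absent from the AE data.

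**Working it through.** **1. Call window.** The Schedule's 1-3 days is 24-72 hours, which matches sections 8.1.3 and 8.1.5. Observation after a puncture can therefore differ by a factor of 72/24 = 3.

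**2. Share of punctures with no later AE-recording visit in the same cycle.** Section 15.1 invites up to about 20% to a repeat visit, in the first year only. Take 100 participants, all 20 invited attending, and no skipped years.

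| Period | Punctures | Followed by a repeat visit | Closing at the call |
|---|---|---|---|
| Year 0 | 100 + 20 = 120 | 20 (16.7%) | 100 (83.3%) |
| Years 0-3 | 4 × 100 + 20 = 420 | 20 (4.8%) | 400 (95.2%) |

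With fewer repeat visits the last column rises: at 10% attendance it is 100/110 = 90.9% and 400/410 = 97.6%.

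**3. Length of the gap, first cycle, no repeat visit.** The next screening falls 12 ± 2 = 10 to 14 months after the first. The call falls between 1 + 1 = 2 days and 30 + 3 = 33 days (about 1.1 months) after screening. The gap is therefore about 10 − 1.1 = 8.9 months at the shortest and just under 14 at the longest, or roughly 9 to 14 months. Skipped years lengthen it. After a repeat puncture (day 28-56) it is about one to two months shorter.

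**4. Do other sections close the gap?**

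- *Section 14.1* has the investigator ask about AEs at each visit after Annual Screening. That matches the Schedule marks and states no look-back to the previous year's puncture.
- *Section 14.2* carries AEs as well as SAEs to the final visit of an enrollment, but says so for participants who enroll more than once. Its general window, to study exit, is for SAEs.
- *Sections 8.1.3, 8.1.5 and 14.4* require follow-up of related AEs once reported. They do not pick up an onset after the call.
- *Section 8.1.1* updates medical history at screening only from the last Enroll-HD visit, which criterion 1.d in 7.1.1 places within the preceding three months. It need not reach a puncture about a year earlier.

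None of these clearly supplies a route. If 14.1 or 14.2 is meant more broadly, it conflicts with 8.1 and sites may apply different windows.

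**5. Possible size (assumption only).** Let f be the share of headaches that start after the call and go unrecorded. Then true rate = recorded rate / (1 − f). The protocol gives no f. For hypothetical recorded rates of 6% and 9%:

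| Assumed f | Recorded 6% | Recorded 9% |
|---|---|---|
| 5% | 6.3% | 9.5% |
| 10% | 6.7% | 10.0% |
| 20% | 7.5% | 11.3% |
| 30% | 8.6% | 12.9% |

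The 4.2.1 percentages come without numerators or denominators and cannot be reproduced. The values above only illustrate the formula and do not correct those rates.

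**The case against.** The strongest reply is that the gap is narrow and the protocol has no settled short window at all.

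- **Some punctures are followed up.** Repeat attendees have AEs recorded at 4-8 weeks and a second call. A reader might infer that no later visit ever records what followed; the parenthesis in 8.1 rules that out. This stands, and it is why the point is limited to most punctures.
- **Other sections read more widely.** Sections 14.1 and 14.2 can be taken to go beyond the call, and 14.4 requires all AEs to be recorded. It would therefore be too strong to say that late events can never enter the data. What can be said is that no clear route is planned. The competing wording is a further reason to reconcile the text.
- **Only non-serious late onsets are affected.** A related headache reported at the call is followed until it resolves or stabilises, and 14.2 has SAEs documented to study exit. This stands.
- **There is no safety endpoint.** The objectives are sample collections and clinical data, and no comparison of headache rates by site or cohort is planned. This also stands: headache is not a defined main safety measure. Since AE start times are recorded, rates could be cut at a common 24 hours, but that would not recover events after the call.
- **The remedy relies on recall.** Asking about mild headaches up to a year later is imperfect. This is true, and it is the reason for reporting the two rates separately.

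**Conclusion.** The gap holds for non-serious events that begin after the call when no repeat visit follows. That is about 83% of punctures in year 0 and 95% over years 0-3, assuming 20% repeat attendance and no skipped years. The unobserved period is roughly 9 to 14 months in the first cycle. Procedure-related rates collected under this version may be understated. They will be if any such event starts after the call and goes unrecorded, but the amount cannot be estimated from the protocol.

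A reader might go further and conclude that the 6% and 9% headache rates in 4.2.1 are biased low. The protocol does not support that. Those rates come from the first two years of a study that enrolled its first participant in January 2017. The present longitudinal design dates from October 2021, and the AE window then in force is not shown.

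The primary objective, a CSF collection, is untouched. This is an inexpensive improvement to safety data that sites already have occasion to collect.

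**What to change.** 1. Reconcile the AE windows in sections 8.1, 14.1 and 14.2, so that one statement governs non-serious events.
2. In 8.1, extend recording of procedure-related AEs to the next study visit.
3. Add an AE mark at Annual Screening in Years 1-3, to record onset, severity, duration and treatment of any event since the last puncture, including whatever is disclosed under criteria n and o.
4. Record the date and time of each follow-up call.
5. Report procedure-related rates to the call and to the next visit separately.

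The cost is one mark in the Schedule, a sentence or so in 8.1, matching edits in section 14 and an eCRF field. No visit or procedure is added. The drawbacks are imperfect recall over about a year, especially for mild headache, and that participants who do not return remain unobserved. The rate to the next visit should be presented with both limits stated.
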